9.2 Risks of study procedures

Blood draws: The risks of blood draws include bleeding, bruising, discomfort, fainting and lightheadedness infection or pain at the needle site. All research personnel and hospital staff drawing blood are trained in the procedure and are familiar with proper infection control protocol. We anticipate that most of the assessments needed as part of the study will already be obtained on clinical grounds and that the need for additional blood draws specific for this research study will be minimal.

9.3 Adequacy of protection against risks

Each participant in this study will be informed of the intent of the study and asked to sign an IRB approved informed consent form. The consent form will fully describe the procedures, risks, alternatives, and potential benefits of the study. Consent will be obtained from eligible participants by a physician investigator or by the study research coordinator. The participants will be given the opportunity to refuse to participate in the study, under the assurance that such refusal will in no way affect their regular treatment. All questions asked by study subject will be answered to the best of the knowledge of the investigator and the study staff. Time will be given for the patient to read the consent form and ask questions prior to performing any study procedures. A copy of the signed and dated consent form will be given to subject. Details of the informed consent process for this study are provided in Section 6.3. There are no alternatives in this study other than not to participate. Potential risks and benefits will be thoroughly explained to the subjects participating and they are free to withdraw from this study at any point in time prior to or during the course of these investigations.

All information, data, etc., collected as a result of these studies is considered confidential and

will be released only as required by law. Information published as a result of this study will be protected completely preserving the anonymity of the participants. Per the Health Insurance Portability and Accountability Act (HIPAA) guidelines, research records will be stored in a locked room identified specifically as a patient record room. All transmitting of data is done by coded names and does not identify any types of names (first or last). Results of any procedures or tests will also be de-identified so as to hide the true identity of patient's names or any other identifiers. On occasion, it may be necessary, for legal reasons, or for good clinical practice, for third parties such as the IRB or DSMB members to review medical records that are identified by name. This however would be on special occasions and would not be a common occurrence. Every effort in all areas of care will be made to keep the patient's information as confidential as possible. As noted above, we will minimize risks to human subjects by creating and maintaining a standard of excellence such as we had with our previous clinical trials at our site. Such standard includes active interactions between faculty and staff on a weekly formal basis, and as needed otherwise, careful attention to training of staff in procedures and their possible complications, and a philosophy of 'patient first' in all of our dealings. Specifically, we use only trained personnel to perform procedures. The plan to handle adverse events is described in detail in the section of data and safety monitoring plan.

9.4 Plans for assuring compliance with safety guidelines and regulations

All clinical staff will be required to participate in training offered through their respective Institutional Review Boards. Training is also required in HIPAA in order to have access to study subject records. International Conference of Harmonization (ICH) Good Clinical Practice (GCP) Guidelines are utilized daily in the clinical research practice and are reviewed periodically. The clinical research teams will have weekly conference calls to provide an opportunity for staff to review and discuss the activities of the study. All clinical and laboratory staff are required to take courses handling blood borne pathogens on a yearly basis as well as training in laboratory safety, handling of biohazards, storage and shipping of clinical and laboratory specimens including dangerous goods.

10. Benefits

10.1 Benefits of the investigational agent

As with other randomized, placebo-controlled studies, there may or may not be any benefits for the subject participating in the study. However, participation in this study will provide additional data on the safety and effectiveness of sirolimus for the treatment of hospitalized patients with COVID-19. The information learned from this research study may benefit other subjects with COVID-19, or other similar viral illnesses, in the future. Subjects who participate in the study will receive all study medications at no charge. The laboratory parameters that are obtained strictly for research purposes will not be billed to the patient or their insurance carrier(s).

10.2 Importance of the knowledge to be gained

The knowledge gained from this study may benefit many subjects with COVID-19, and other similar viral illnesses. The information obtained may improve the scientific community's understanding of the management of COVID-19. Specifically, the study will identify the safety and efficacy of sirolimus in hospitalized patients with COVID-19 and thus may alter the clinical approach to patients with this and other similar viral diseases.

[figure not shown]
10.3 Benefits of Study Procedures

None.

11. Study Drug

11.1 Sirolimus or Placebo

Sirolimus is a macrocyclic lactone produced by *Streptomyces hygroscopicus*. The chemical name of sirolimus (also known as rapamycin) is (3S,6R,7E,9R,10R,12R,14S,15E,17E,19E,21S,23S,26R,27R,34aS)-9,10,12,13,14,21,22,23,24,25,26,27,32,33,34,34a-hexadecahydro-9,27-dihydroxy-3-[(1R)-2-[(1S,3R,4R)-4-hydroxy-3-methoxycyclohexyl]-1-methylethyl]-10,21-dimethoxy-6,8,12,14,20,26-hexamethyl-23,27-epoxy-3H-pyrido[2,1-c][1,4]oxaazacyclohepten-1,5,11,28,29 (4H,6H,31H)-pentone. Its molecular formula is C₅₁H₇₉NO₁₃ and its molecular weight is 914.2. The structural formula of sirolimus is:

Sirolimus is a white to off-white powder and is insoluble in water, but freely soluble in benzyl alcohol, chloroform, acetone, and acetonitrile. Sirolimus is available for administration as an oral solution containing 1 mg/mL sirolimus. Sirolimus is also available as a white, triangular-shaped tablet containing 1 mg sirolimus, and as a yellow to beige triangular-shaped tablet containing 2 mg sirolimus. The inactive ingredients in sirolimus Oral Solution are Phosal 50 PG® (phosphatidylcholine, propylene glycol, mono- and di-glycerides, ethanol, soy fatty acids, and ascorbyl palmitate) and polysorbate 80. Rapamune Oral Solution contains 1.5% - 2.5% ethanol. The inactive ingredients in sirolimus tablets include sucrose, lactose, polyethylene glycol 8000, calcium sulfate, microcrystalline cellulose, pharmaceutical glaze, talc, titanium dioxide, magnesium stearate, povidone, poloxamer 188, polyethylene glycol 20,000, glyceryl monooleate, carnauba wax, and other ingredients. The 2 mg dosage strength also contains iron oxide yellow 10 and iron oxide brown 70.

The placebo for the tablet is lactose powder contained in a gel capsule. All tablet medication will be over-encapsulated to maintain the blind. The placebo for the Rapamune Oral Solution is 0.9% normal saline solution.

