5.5 Study Drug Treatment

Patients who meet eligibility criteria, provide informed consent and are enrolled in the study will be randomized to receive sirolimus or placebo in a double-blind manner and a 2:1 randomization scheme in favor of sirolimus. The sirolimus dose for the study will be 6mg daily on day 1 followed by 2mg daily for a maximum treatment duration of 14 days, or until hospital discharge, whatever happens first. The study drug will be provided by the drug manufacturer, Pfizer, encapsulated and dispensed by the University of Cincinnati's Investigational Drug Services (IDS) Pharmacy, and given to the patients by their bedside nurse. Patients will be reminded about the side effects of sirolimus. Every attempt will be made to give the medication at the same time every day. Chart reviews will be conducted on a daily basis to determine changes in clinical status, concomitant medications and laboratory parameters. Study specific biomarkers will be measured at baseline and then at days 3, 7 and 14. Section 6.2 provides a detailed description of the study specific schedule of events. Patients will be instructed to

contact the study staff should they experience any side effects. Study drug may be held or reduced in the event of unacceptable side effects.

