12.1 Modification of investigational product

The tablet form of the investigational product will be overencapsulated to maintain the blind. The liquid solution will be matched with a liquid placebo solution that has an identical appearance. Placebo capsules are prepared by filling the capsule body with lactose powder.

For majority of the subjects, sirolimus will be administered in the tablet formulation. However, in some subjects this may be substituted to the oral solution while maintaining blinded randomization as clinically indicated, e.g. in patients who have progressed to require advanced respiratory support and cannot take oral pills, the liquid solution may be administered via a feeding tube.

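### Section 12.1 says the liquid placebo looks identical to the active solution, but Section 11.1 makes it plain saline; the blind is at risk for the minority given liquid

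*Combined protocol and SAP*

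**What the plan says.** The trial is described as double-blind (protocol Section 5). Section 11.1 gives the composition of both liquids. For the comparator: "The placebo for the Rapamune Oral Solution is 0.9% normal saline solution". For the active solution, the vehicle is "phosphatidylcholine, propylene glycol, mono- and di-glycerides, ethanol, soy fatty acids, and ascorbyl palmitate", together with polysorbate 80, and "Rapamune Oral Solution contains 1.5% - 2.5% ethanol".

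Section 12.1 then describes the pair as matched: "The liquid solution will be matched with a liquid placebo solution that has an identical appearance". It sets out when liquid is used. "For majority of the subjects, sirolimus will be administered in the tablet formulation", but "in some subjects this may be substituted to the oral solution while maintaining blinded randomization as clinically indicated". The single example is a patient who has progressed to advanced respiratory support and cannot swallow pills, for whom "the liquid solution may be administered via a feeding tube".

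Section 5.5 says study drug is "given to the patients by their bedside nurse". The blinding step in Sections 11.1 and 12.1 that conceals appearance, over-encapsulation, applies to tablets only. The SAP says nothing about formulation or blinding.

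**The concern.** The protocol claims a blinding property for the liquid that its own composition list does not support. Saline contains none of the lipid, glycol, alcohol or surfactant components listed for the active solution. If the two can be told apart by eye, the person preparing or giving the dose may infer the arm.

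What is at stake is the part of the follow-up that depends on judgement. Once a patient has progressed, treating clinicians decide on other rescue therapies (Section 4.3) and on whether to continue study drug, withdraw the patient or unblind (Sections 6.1 and 7.1). Time on advanced support and hospital stay depend partly on such decisions. The investigator or a designee assigns adverse-event attribution (Section 14.7), and withdrawal for intolerance or a drug-related event is counted as treatment failure (Section 13.1.4). Knowledge of the arm could influence any of these.

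**Working it through.** The plan states no figure on this point, so the check is mainly a comparison of sections, followed by simple arithmetic for scale.

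**Step 1. Composition against claim.**
- Active liquid (Section 11.1): phospholipid, propylene glycol, glycerides, ethanol at 1.5% to 2.5%, soy fatty acids, ascorbyl palmitate, polysorbate 80.
- Placebo liquid (Section 11.1): 0.9% saline.
- Claim (Section 12.1): identical in appearance. Smell, taste and viscosity are not claimed to match.
- Result: no listed vehicle component is shared. A visual match is implausible on these lists, and no statement elsewhere supports it.

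**Step 2. Is there another safeguard?**
- Tablets: over-encapsulated, with lactose-filled capsules as placebo (Sections 11.1 and 12.1).
- Dose changes: mirrored in a placebo subject (Section 12.3.2).
- Liquid: no opaque syringe, colouring, vehicle-matched placebo or other masking is described.
- Result: the gap is specific to the liquid.

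**Step 3. Who could see it?**
- The bedside nurse gives the drug (Section 5.5). A feeding tube spares the patient the taste but does not hide the liquid from the nurse.
- When the administration record is unclear, the compliance check may go to the bedside nurse (Section 11.4), which is one route by which a guess could reach study staff.

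**Step 4. When, relative to the primary endpoint?**
- In the example in Section 12.1, progression to advanced support has already happened, so the primary event is already recorded.
- Progression is given only as an example under a general clinical-indication clause, so earlier use is allowed. The documents give no rate for it.

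**Step 5. How many patients?** Inputs: 30 patients randomised 2:1 (Section 5), hence 30 × 2/3 = 20 sirolimus and 30 × 1/3 = 10 placebo; planning progression rates of 50% on placebo and 25% on sirolimus (Section 15 and the SAP).
- Placebo progressors: 10 × 0.50 = 5.
- Sirolimus progressors: 20 × 0.25 = 5.
- Total: 5 + 5 = 10, and 10/30 = 33%.

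This is a ceiling for the post-progression example at those rates. Liquid also requires that the patient cannot take pills, and the endpoint includes high-flow oxygen and CPAP, where the documents do not say that swallowing is lost. Some progressors may be withdrawn, or reach day 14 or discharge, without receiving liquid. Use before progression is not counted and would add to the total. The ceiling moves with the rates: with no drug effect and 50% in both arms it would be 30 × 0.50 = 15. At the planning rates the possible exposure also differs by arm, half of placebo against a quarter of sirolimus.

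**The case against.** Three stronger readings are tempting, and the documents support none of them.

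- **Patients on liquid are effectively unblinded.** No section gives the colour, clarity, viscosity, smell or taste of either liquid. Going from an ingredient list to knowledge of the arm is an inference. In the only example the dose goes through a tube, so the patient need not see or taste it. Nor does any section say how the treating clinician would come to see the liquid; the route through the nurse is plausible but not documented.
- **The primary endpoint is compromised.** In the example given, the primary event precedes the switch. Earlier use is permitted, but how often it would happen is unknown.
- **A third of the trial loses its blind.** Ten of 30 is the number expected to progress, not the number expected to receive liquid. Section 12.1 says most subjects take tablets.

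Two further points on the other side are fair. The blind after progression is already conditional, because Sections 6.1, 7.1 and 12.3.2 allow withdrawal with or without unblinding, and Section 7.1 leaves open-label sirolimus after unblinding to the clinician. The outcomes most exposed also rank low: Section 4.3 lists rescue therapy, duration of advanced support and hospital stay under other outcome measures, and withdrawal is not an endpoint at all.

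These points limit the size of the problem. They do not remove the conflict between Sections 11.1 and 12.1. Permission to unblind a patient deliberately is also different from an unrecorded loss of masking in patients who remain in the blinded study.

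**Conclusion.** The point holds in a limited form. The identical-appearance claim in Section 12.1 is unsupported and, on the compositions in Section 11.1, implausible. With no masking described for the liquid, the blind is at risk for the minority who receive it, chiefly through the bedside nurse and from there the care team. Actual unblinding is not shown.

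The main exposure is after progression, in rescue therapy, duration of advanced support, hospital stay, adverse-event attribution, and decisions on withdrawal or unblinding. The primary endpoint is exposed only through liquid given before progression, which is allowed but not quantified.

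The ceiling for the post-progression example is about 10 of 30 patients, assuming that the planning rates hold and that every progressor is switched. The second assumption is certainly generous, so the realistic number is lower, but the documents do not allow an estimate. This should be corrected because the remedy is cheap; it is not a reason to doubt the design as a whole.

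**What to change.** Reconcile Sections 11.1 and 12.1 by one of the following:

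1. Use a liquid placebo made to match the active vehicle, and describe it in Section 11.1.
2. Keep saline, but have the investigational pharmacy dispense both liquids in opaque, pre-filled enteral syringes, and state this in Section 12.1.
3. If neither is feasible, delete the identical-appearance claim, record the formulation and the date of any switch on the case report form, and report outcomes after a switch as potentially unblinded.

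Recording formulation and switch date is worth doing under any option, since it shows how many patients received liquid and whether any did so before progression.

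Options 1 and 2 cost a small amount of extra preparation for a minority of patients, in a pharmacy that already encapsulates and dispenses study drug. Option 3 costs wording and two data fields. None changes the sample size, the endpoints or the dosing.

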11.2 Pharmacokinetics of sirolimus in humans

Absorption: Following administration of sirolimus oral solution, the mean times to peak concentration (t_{max}) of sirolimus are approximately 1 hour and 2 hours in healthy subjects and renal transplant patients, respectively. The systemic availability of sirolimus is low, and was estimated to be approximately 14% after the administration of the oral solution. In healthy subjects, the mean bioavailability of sirolimus after administration of the tablet is approximately

27% higher relative to the solution. Sirolimus tablets are not bioequivalent to the solution; however, clinical equivalence has been demonstrated at the 2mg dose level.²⁸

Distribution: The mean (\pm SD) blood-to-plasma ratio of sirolimus was 36 ± 18 in stable renal allograft patients, indicating that sirolimus is extensively partitioned into formed blood elements. The mean volume of distribution of sirolimus is 12 ± 8 L/kg. Sirolimus is extensively bound (approximately 92%) to human plasma proteins, mainly serum albumin (97%), α 1-acid glycoprotein, and lipoproteins.²⁸

Metabolism: Sirolimus is a substrate for both CYP3A4 and P-gp. Sirolimus is extensively metabolized in the intestinal wall and liver and undergoes counter-transport from enterocytes of the small intestine into the gut lumen. Inhibitors of CYP3A4 and P-gp increase sirolimus concentrations. Inducers of CYP3A4 and P-gp decrease sirolimus concentrations. Sirolimus is extensively metabolized by O-demethylation and/or hydroxylation. Seven major metabolites, including hydroxy, demethyl, and hydroxydemethyl, are identifiable in whole blood. Some of these metabolites are also detectable in plasma, fecal, and urine samples. Sirolimus is the major component in human whole blood and contributes to more than 90% of the drug's activity.²⁸

Elimination: After a single dose of [14 C] sirolimus oral solution in healthy volunteers, the majority (91%) of radioactivity was recovered from the feces, and only a minor amount (2.2%) was excreted in urine. The mean \pm SD terminal elimination half-life ($t_{1/2}$) of sirolimus after multiple dosing in stable renal transplant patients was estimated to be about 62 ± 16 hours.²⁸

11.3 Accountability of Investigational Product

Under Title 21 of the Code of Federal Regulations (21CFR §312.62) the investigator will maintain adequate records of the disposition of the investigational product(s)/intervention material(s), including the date and quantity of the drug received, to whom the drug was dispensed (participant-by-participant accounting), and a detailed accounting of any investigational product(s)/intervention material(s) accidentally or deliberately destroyed. Records for receipt, storage, use, and disposition will be maintained by the University of Cincinnati's IDS Pharmacy located at the study site. A dispensing log will be kept current for each participant. This log will contain the identification of each participant and the date and quantity of investigational product(s)/intervention material(s) dispensed. All records regarding the disposition of the investigational product will be available for inspection by the DSMB, IRB or other appropriate monitoring bodies.

11.4 Assessment of compliance with the investigational product

Assessment of compliance will be done by daily review of the medication administration record (MAR) in the study subject's medical chart. In case of lack of absolute clarity regarding study drug administration based on MAR review, contact will be made with one or all of the following: patient's bedside nurse, investigational pharmacy, and the study subject, in order to determine if the daily dose of the study drug was administered.

12. Modification or discontinuation of the investigational product

12.1 Modification of investigational product

The tablet form of the investigational product will be overencapsulated to maintain the blind. The liquid solution will be matched with a liquid placebo solution that has an identical appearance. Placebo capsules are prepared by filling the capsule body with lactose powder.

For majority of the subjects, sirolimus will be administered in the tablet formulation. However, in some subjects this may be substituted to the oral solution while maintaining blinded randomization as clinically indicated, e.g. in patients who have progressed to require advanced respiratory support and cannot take oral pills, the liquid solution may be administered via a feeding tube.

12.2 Premature discontinuation of investigational product

Refer to Sections 7.1, 12.3 and 13.1.

12.3 Medication adjustments

12.3.1 Dose Delays

For patients who are unable to tolerate the protocol-specified dosing schedule, dose adjustments are permitted in order to keep the patient on study drug. If administration of sirolimus must be interrupted because of unacceptable toxicity, drug dosing will be interrupted or modified according to rules described in Section 12.3.2. Given the short trial duration, this will likely result in participant withdrawal from the study. Sirolimus therapy may also be interrupted to accommodate surgical procedures or other invasive therapies at the discretion of treating clinicians. Major Events are non-treatment-related grade 3 and 4 pulmonary and non-pulmonary toxicities. Treatment should be delayed for major events if sirolimus may further complicate the non-treatment related event. If a major event requires a delay of treatment, treatment must be delayed until toxicity is resolved (\leq Grade 1 or \leq Baseline). For treatment-related toxicities and major events, if toxicity is not resolved in \leq 4 weeks, patient will be taken off the treatment that is most likely to be related to the toxicity.

